9.6.7 Physical Measurements

Summary statistics for baseline, minimum on study, maximum on study, EOTP, and change from baseline to EOTP by treatment group will be provided for:

• Weight

No other physical measurements will be summarized but the data will be captured in the electronic line listings.

9.6.8 Electrocardiogram

The electrocardiogram (ECG) measurements from this clinical study were performed as per standard of care for routine safety monitoring, rather than for purposes of assessment of potential QT interval corrected (QTc) effect. Because these evaluations may not necessarily be performed under the rigorous conditions expected to lead to meaningful evaluation of QTc data; neither summaries nor statistical analyses will be provided, and these data would not be expected to be useful for meta-analysis with data from other trials.

9.6.9 Antibody Formation

The number and percentage of subjects with confirmed neutralizing antibody formation to darbepoetin alfa **and erythropoietin** will be presented.

9.6.10 Exposure to Investigational Product

Exposure to investigational product endpoints will include dose duration in weeks (the study week of last dose plus 3), the number of doses, the cumulative dose

administered (µg), the weight-adjusted cumulative dose administered (cumulative dose divided by the baseline weight), the average weekly dose (cumulative dose divided by the dose duration), the average dose administered (cumulative dose divided by the number of doses), the weight-adjusted average weekly dose (weight-adjusted cumulative dose divided by the dose duration), and the weight-adjusted average dose administered (weight-adjusted cumulative dose divided by the number of doses).

Change in dosing will include the number and percent of subjects who had a dose reduction because of a **fast** rate of **hemoglobin** rise, had a dose withheld because the hemoglobin threshold was surpassed, had dose discontinued because of a severe or life-threatening adverse event reported by the investigator to be related to investigational product, and **subjects** switched to placebo because of non-response (darbepoetin alfa group only).

Descriptive statistics will be produced to describe the exposure to investigational product by treatment group (only the dose duration and the numbers doses will be summarized for the placebo group).

 To assess the impact of the early termination of the study, the analysis of exposure to investigational product endpoints and change in dosing will be repeated for subjects who were still on-study or in long-term follow-up as of June 7 and for subjects who were not impacted by the early study termination.

9.6.11Exposure to Other Protocol-specified TreatmentNot applicable

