15. APPENDICES

	Screening ^a	Screening ^a Treatment Period ⁿ			EOTP Visit	LTFU ^m
Study Week	-3	Day 1 / Wk 1	Q3W (± 6 days) (eg, Wk 4, 7, 10, 13, 16, 19, 22, 25, 28)	Last dose of IP	Next Q3W visit after disease progression	Every 3 months (± 2 weeks)
Informed consent, medical history, and complete physical exam	х					
Vital signs ; other ^b	Х	Х	Х	X X		
ECOG performance status	Х	Х	Х	Х	Х	
Adverse events ^c , concomitant meds and RBC transfusions						
Tumor evaluation and assessment of disease progression					► ►	
Investigational product administration ^d		Х	Х	Х		
Lab testing						
Central lab clinical chemistries ^e	Х	Х	Х	Х	X °	
Central lab CBC ^f	Х	Х	Х	Х	X°	
Local lab hemoglobin ^g	Х	Х	Х	Х	X°	
Central lab serum folate and vitamin B ₁₂	Х					
Central lab iron studies ^h	Х	Х	Х	Х		
Tumor samples ⁱ	Х					
Darbepoetin alfa antibody ^j		Х			Х	
Endogenous erythropoietin level		Х				
Central lab pregnancy test ^k	Х					
Imaging studies						
CT scan, MRI, or PET-CT ¹	Х	Every 9 weeks until disease progression (eg, Wk 10, 19, 28)				
LTFU						
Collect information on survival, ESA usage, anti-cancer therapy, radiotherapy, anti-cancer surgery						х

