Screening Hemoglobin	The local laboratory hemoglobin value obtained within 7 days prior to randomization; this is used to confirm eligibility and randomization stratum and will be used as a stratification factor for overall survival, progression-free survival, and incidence of transfusions from weeks 5 (ie, day 29) to end of treatment
Study Day 1.	This is the first day of investigational product administration. All laboratory assessments on study day 1 are to be completed before study drug administration and will be used as baseline measurements. The randomization day may occur on the same day as the first dose of investigational product or it may occur up to 4 days before the first dose of investigational product
Study Entry Hemoglobin	The hemoglobin value obtained closest to the date when the subject signs and dates the informed consent form (ICF). This may be a central or local laboratory hemoglobin value.

Abbreviation or Term	Definition/Explanation
Study Termination Date	The planned study termination date will be the date when the 2700 th death is reported in the clinical trial database or at an early termination date, if applicable . Once this death is reported or the early termination date is reached, sites will be instructed to enter all outstanding data into the clinical trial database, the database will be cleaned, a snapshot will be taken, the database will be locked, and the primary analysis will be performed. Any additional deaths reported during the entry of outstanding data which occur on or prior to the termination date will be counted in the primary analysis.
Study Week 1	The 7-day period beginning with study day 1 is considered study week 1.
Treatment Period	The treatment period begins on study day 1 and ends at the next Q3W visit following disease progression. Subjects who are unable to continue Q3W visits and Q9W imaging studies until progression should complete EOTP procedures no later than their next Q3W visit (± 6 days).
TVE	Thrombovascular event
VTE	Venous thromboembolic event

1. Introduction

The purpose of this Statistical Analysis Plan (SAP) is to provide details of the statistical analyses that have been outlined within the protocol for study 20070782, darbepoetin alfa dated 14 September 2017. The scope of this plan includes the **planned final** analysis and will be executed by the Amgen Global Biostatistics department unless otherwise specified.

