3.1 Study Design

This is a double-blind, randomized, placebo-controlled, phase 3 study in CIA subjects receiving multi-cycle chemotherapy for the treatment of advanced stage NSCLC cancer. Randomization will occur in a 2 to 1 ratio (darbepoetin alfa to placebo) and will be stratified by histology (squamous versus other), screening hemoglobin (< 10.0 g/dL versus \geq 10.0 g/dL), and geographic region (see Section 4.1 for regions).

Subjects will receive IP Q3W during the treatment period. IP will be discontinued within 3 weeks after the completion of chemotherapy, or upon the determination of disease progression, whichever occurs first. Study visits Q3W and imaging studies Q9W will occur during the treatment period until disease progression.

An end of the treatment period visit will occur at the next Q3W visit after disease progression has been determined. **Hemoglobin and other hematology and chemistry values collected beyond this period (ie, beyond 3 weeks after disease progression) will be excluded from analysis.** Subjects will then enter long term follow-up and will be followed for survival until death, until approximately 2700 deaths have occurred **or until early study termination**.

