Details of analyses provided to the Data Monitoring Committee, including the planned interim analyses, are not described or analyzed directly under this plan. These analyses were generated by PRA Health Sciences, Charlottesville, Virginia. An unplanned interim analysis conducted by an independent group at Amgen in Q4 2016 is also not covered in this plan.

14. Appendices

Appendix A. Technical Detail and Supplemental Information Regarding Statistical Procedures and Programs

Visit	Study day(s)	Window Definition	Interval (days)
Screening period	"-1"	Evaluation(s) within 21 days prior to the randomization date	21 to day -1
		Note: these should be on or after the date of consent, and should include history, vital sign, ECOG and other protocol specified measurements	
Randomization	-4 to 1	Randomization may occur on study day 1 or up to 4 day prior to study day 1.	1 day
		Note: Adverse events will be reported beginning from the data of randomization	
		Note: Subjects who progressed in the screening period (or prior to the screening period) are not eligible for randomization (protocol Section 7.1.6)	
Baseline/Study Day 1	1	Evaluation on Study Day 1 or last evaluation prior to Study Day 1 (if no value is available on Study Day 1). The first dose of study drug should be given on study day 1	1
		Note: Baseline hemoglobin value should be a central laboratory value. Note that a local laboratory hemoglobin value may be present in the database; this is used to confirm study eligibility and should not be used a the baseline hemoglobin value	
Treatment	Every 21	Dose 1: study day 1 (1-7)	Every 21
Period (Q3W visits)	days (+/- 6 davs)	Dose 2: study day 22 (15-27)	days(15-27 davs);
,	,	Dose 3: study day 43 (37-49)	duration is
		Dose 4: study day 64 (58-70)	n/u
		Dose 5: study day 85 (79-91)	
		Dose 6: study day 106 (100-112)	
		Dose 7: study day 127 (121-133)	
		Dose 8: study day 141 (135-147)	
		Dose 9: study day 162 (156-168)	
		Dose 10: study day 183 (177-189)	

	etc	
	Note: The treatment period, including study drug administration should last until disease progression	
	Note: Per protocol, study procedures (eg, ECOG, laboratory sample draws) may be performed up to 1 day prior to IP dosing	

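### SAP 9.6.10 counts dose duration one week too long for on-schedule dosing, which understates the average weekly dose by 25% after one dose and 7.7% after four

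*SAP*

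**What the plan says.** SAP 9.6.10 sets out the exposure endpoints. It defines "dose duration in weeks (the study week of last dose plus 3") and then "the average weekly dose (cumulative dose divided by the dose duration"). The weight-adjusted average weekly dose uses the same denominator. The averages per dose administered are divided by the number of doses instead. For placebo, only dose duration and number of doses are summarized.

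The week count comes from the SAP's list of abbreviations and definitions. Under Study Week 1: "The 7-day period beginning with study day 1 is considered study week 1". Under Study Day 1: "This is the first day of investigational product administration". So the first dose is always in week 1.

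The interval is three weeks (SAP 3.1: "Subjects will receive IP Q3W during the treatment period"). The schedule in Protocol Appendix A places the visits after day 1 at "eg, Wk 4, 7, 10, 13, 16, 19, 22, 25, 28". SAP Appendix A gives the matching days, for example "Dose 4: study day 64 (58-70").

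**The concern.** Adding three weeks to the time of the last dose looks like the natural way to credit that dose with its full interval. It works only if the week of the last dose is a count of weeks elapsed since the first dose: 0, 3, 6 and so on. The SAP's weeks run 1, 4, 7, so the week number already includes the first of the three weeks that the last dose covers. Adding 3 counts that week twice.

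The surplus week goes into dose duration in both arms and, as a denominator, into the average weekly and weight-adjusted average weekly dose. Average weekly dose is a summary the protocol itself lists (Protocol 10.6.3), and readers use it to relate the safety results to the dose given. The proportional error is largest for short courses. SAP 9.6.10 repeats the exposure analysis for subjects affected and not affected by the early termination. If those groups differ in number of doses, part of any difference in weekly dose would come from the formula.

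**Working it through.** The documents give a formula but no exposure figure, so there is no stated number to reproduce first.

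**Inputs**
- First dose on study day 1, in study week 1; no week 0 is defined (SAP definitions).
- Week numbering confirmed by the transfusion endpoint, which equates week 5 with day 29: 4 × 7 + 1 = 29 (SAP 2.1).
- Doses every 3 weeks, in weeks 1, 4, 7, 10 and so on (Protocol Appendix A). SAP Appendix A agrees: days 1, 22, 43 and 64 are the first days of those weeks. That table steps by 14 days rather than 21 between dose 7 (day 127) and dose 8 (day 141), so it is used here only for the early doses.
- 500 µg per dose, for illustration. The percentages do not depend on it.

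**On-schedule dosing**

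For k doses with none missed, the last dose is in week w = 1 + 3(k − 1).
- SAP duration: w + 3 = 3k + 1 weeks.
- Weeks covered, counting w, w+1 and w+2 for the last dose: w + 2 = 3k weeks.
- Understatement of the average weekly dose: 1 − 3k/(3k + 1) = 1/(3k + 1).

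| Doses k | Week of last dose | SAP duration | Weeks covered | SAP µg/week | 500k/3k µg/week | Understated by |
|---|---|---|---|---|---|---|
| 1 | 1 | 4 | 3 | 125.0 | 166.7 | 25.0% |
| 2 | 4 | 7 | 6 | 142.9 | 166.7 | 14.3% |
| 3 | 7 | 10 | 9 | 150.0 | 166.7 | 10.0% |
| 4 | 10 | 13 | 12 | 153.8 | 166.7 | 7.7% |
| 6 | 16 | 19 | 18 | 157.9 | 166.7 | 5.3% |
| 10 | 28 | 31 | 30 | 161.3 | 166.7 | 3.2% |

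The one-dose row is exact for any subject with a single dose, because that dose is on day 1 by definition. Dose reductions change the cumulative dose but not the percentage.

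**Off-schedule dosing**

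Protocol 6.1.3 allows ±6 days. Let d be the study day of the last dose and j its day within the study week (1 to 7). The exact duration is (d − 1 + 21)/7 weeks. The SAP's overcount is then

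ceil(d/7) + 3 − (d + 20)/7 = (8 − j)/7 weeks.

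This runs from 1 week (j = 1, every on-schedule dose) to 1/7 week (j = 7). It is always positive.

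- Second and last dose on day 28: SAP 7.00 weeks against 48/7 = 6.86, an understatement of about 2%.
- Fourth and last dose on day 58: SAP 12 against 78/7 = 11.14 weeks, 7.1%.
- Fourth and last dose on day 64: 13 against 84/7 = 12.00, 7.7%.
- Fourth and last dose on day 70: 13 against 90/7 = 12.86, 1.1%.

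**The case against.** The strongest reply is that little depends on this. SAP 9.6.10 asks for descriptive statistics only, and no hypothesis test or decision rule uses dose duration. Cumulative dose, number of doses and average dose administered are all reported correctly, so a reader can still see how much drug was given. Both arms use the same formula, so with on-schedule dosing the between-arm difference in duration is unchanged. Exposure is also not among the first-priority outputs in SAP section 12. All of this stands. It limits the consequence but does not make the formula right.

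A second reply is that duration may be a convention. Nothing in the documents supports that: no week 0 is defined, and no other definition makes the added 3 correct. The plan's own end of the efficacy treatment period runs 21 days from the last dose of investigational product or chemotherapy, whichever is later, which fits a three-week credit for the last dose.

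Three stronger readings might be inferred, and the documents do not support them.
- **Every subject is overcounted by a full week.** In whole study weeks, yes. In exact days the excess can be as small as 1/7 week.
- **The formula can never return 166.7 µg/week.** It can. A second 500 µg dose on days 16 to 21 is within the window and falls in study week 3, so the SAP duration is 6 weeks and 1000/6 = 166.7. That duration is still too long in exact days (day 21: 41/7 = 5.86 weeks).
- **The summaries will show weekly dose rising with longer treatment.** The formula does penalize short courses more. But Protocol 6.1.2 reduces or withholds doses as hemoglobin rises and switches non-responders to placebo, which lowers the actual weekly dose over time. The artefact might only blunt a real decline.

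**Conclusion.** The definition in SAP 9.6.10 conflicts with the SAP's own week numbering. For on-schedule dosing it overstates dose duration by one week and understates the average weekly and weight-adjusted average weekly dose by 1/(3k + 1).

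The 25% figure for one dose needs no scheduling assumption. The figures for two or more doses assume doses on the nominal days with none missed or withheld. With a last dose later in its study week, the error is smaller but in the same direction. All figures credit the last dose with its 21-day interval.

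The error is proportionally larger for short courses, and nothing beyond that about trends is shown. Three descriptive outputs are affected: dose duration in both arms and the two weekly-dose averages. This is worth correcting because average weekly dose is a protocol-listed summary that would be reported with wrong values, but it does not bear on the survival, progression or transfusion conclusions.

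**What to change.** In SAP 9.6.10, define dose duration in weeks as (study day of last dose − 1 + 21)/7, and state that the average weekly and weight-adjusted average weekly doses are derived from it. One dose then gives 21/7 = 3 weeks and 500/3 = 166.7 µg/week; four on-schedule doses give 84/7 = 12 weeks and 2000/12 = 166.7 µg/week.

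The day-based form is preferable to changing the added 3 to a 2. The two agree when the last dose is on the first day of a study week, but differ by up to 6/7 week otherwise: for a last dose on day 28 they give 6.86 and 6.00 weeks.

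The cost is one phrase in the SAP and one line of code, with no new data. SAP 7.2 describes database lock as still to come, so the change can be made before the outputs are produced.

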9.6.12 Exposure to Concomitant Medication

Medications of Interest

The concomitant medications of interest will be summarized by preferred term for each treatment group as coded by the World Health Organization Drug (WHODRUG) dictionary as of Q2 2017. The number and proportion of subjects receiving therapies of interest, including erythropoiesis stimulating agents other than investigational product (as defined in the protocol), will be summarized by preferred term or category for each treatment group as coded by the WHODRUG dictionary. For erythropoiesis stimulating agents, summary statistics will be provided to

describe the amount of exposure received by treatment group. See Appendix B for a list of selected medications and their groupings.

Concomitant Chemotherapy

Treatment(s) for NSCLC (including chemotherapy, anti-EGF-R, anti-angiogenic agents, or other anti-cancer treatments) both during the treatment period and until the first disease progression will be summarized, including the amount of exposure received by treatment group.

10. Changes From Protocol-specified Analyses

The following changes to the analysis will be done due to changes in analysis practices during the study duration but are not specified in the protocol:

Summarization of demographic and baseline characteristics will be limited to the primary analysis set; analysis of these data using the radiographic endpoint primary analysis set, transfusion from week 5 to EOTP primary analysis set, full analysis and radiographic endpoint full analysis set will not be done

Sensitivity analyses are limited to the primary and secondary safety and efficacy endpoints

Stratified analyses are reduced to only the primary dataset per current practice

Subset analyses were limited per current practice

Analysis of safety data (adverse events, vital signs, hematology and chemistry data, study drug dosing, other medications, concomitant medications of interest, and antibodies) using a Safety Set and subjects as treated (rather than as randomized) replaced the analysis in the primary data set by randomized treatment group for consistency with the analyses for other clinical trials in the darbepoetin alfa program.

Analysis of adverse events is limited to current Amgen standard adverse events tables (eg, summaries of treatment-related adverse events and treatment-related serious adverse events have been excluded)

Changes from the protocol will also be documented in the Clinical Study Report.

11. Literature Citations / References

12. Prioritization of Analyses

First priority analyses (due within 2-3 business days following database lock):

- Demographics, baseline characteristics, baseline disease characteristics, subject disposition, IPDs (to assess imbalances between treatment groups); cross tabulation of stratification factors in IVRS vs reported using case report forms
- Overall Survival (primary analysis set by randomized treatment group; all subjects and stratified by geographic region, histology and screening hemoglobin) including Kaplan-Meier plot
- Progression-free survival (all subjects in the primary analysis set by randomized treatment group) including Kaplan-Meier plot
- Objective response rate (all subjects in the primary analysis set by randomized treatment group)
- Incidence of RBC transfusions from Week 5 to EOTP or hemoglobin ≤ 8 g/dL (all subjects in the primary analysis set by randomized treatment group)
- Adverse Events (AEs; safety analysis set by actual treatment group; all subjects)
- Serious AEs (AEs; safety analysis set by actual treatment group; all subjects)
- Events of interest (AEs; safety analysis set by actual treatment group; all subjects)
- AEs leading to study drug discontinuation (AEs; safety analysis set by actual treatment group; all subjects)
- Fatal AEs (AEs; safety analysis set by actual treatment group; all subjects)
- VTEs (AEs; safety analysis set by actual treatment group and primary analysis set by randomized treatment group; all subjects)
- Line graph of mean (with 95% confidence limits) hemoglobin values over time (all subjects in the primary analysis set by randomized treatment group)
- Box plot of median hemoglobin values (with 25th and 75th percentiles, minimum and maximum) over time (all subjects in the primary analysis set by randomized treatment group)

13. Data Not Covered by This Plan

Paraffin embedded tumor tissue blocks or unstained tumor slides collected in this study will not be described or analyzed directly and are not included in this plan.

Details of analyses provided to the Data Monitoring Committee, including the planned interim analyses, are not described or analyzed directly under this plan. These analyses were generated by PRA Health Sciences, Charlottesville, Virginia. An unplanned interim analysis conducted by an independent group at Amgen in Q4 2016 is also not covered in this plan.

14. Appendices

Appendix A. Technical Detail and Supplemental Information Regarding Statistical Procedures and Programs

Visit	Study day(s)	Window Definition	Interval (days)
Screening period	"-1"	Evaluation(s) within 21 days prior to the randomization date	21 to day -1
		Note: these should be on or after the date of consent, and should include history, vital sign, ECOG and other protocol specified measurements	
Randomization	-4 to 1	Randomization may occur on study day 1 or up to 4 day prior to study day 1.	1 day
		Note: Adverse events will be reported beginning from the data of randomization	
		Note: Subjects who progressed in the screening period (or prior to the screening period) are not eligible for randomization (protocol Section 7.1.6)	
Baseline/Study Day 1	1	Evaluation on Study Day 1 or last evaluation prior to Study Day 1 (if no value is available on Study Day 1). The first dose of study drug should be given on study day 1	1
		Note: Baseline hemoglobin value should be a central laboratory value. Note that a local laboratory hemoglobin value may be present in the database; this is used to confirm study eligibility and should not be used a the baseline hemoglobin value	
Treatment	Every 21	Dose 1: study day 1 (1-7)	Every 21
Period (Q3W visits)	days (+/- 6 davs)	Dose 2: study day 22 (15-27)	days(15-27 davs);
,	,	Dose 3: study day 43 (37-49)	duration is
		Dose 4: study day 64 (58-70)	n/u
		Dose 5: study day 85 (79-91)	
		Dose 6: study day 106 (100-112)	
		Dose 7: study day 127 (121-133)	
		Dose 8: study day 141 (135-147)	
		Dose 9: study day 162 (156-168)	
		Dose 10: study day 183 (177-189)	

	etc	
	Note: The treatment period, including study drug administration should last until disease progression	
	Note: Per protocol, study procedures (eg, ECOG, laboratory sample draws) may be performed up to 1 day prior to IP dosing	
	Imaging studies will be performed every 9 weeks (± 7 days) or at any time symptoms suggestive of disease progression occur. Subjects who discontinue chemotherapy or IP should continue to be evaluated radiographically Q9W until disease progression.	Every 8-10 weeks until progression
EOTP	The EOTP visit is the next Q3W visit (± 6 days) after disease progression	n/d
Long-term follow-up (LTFU)	 LTFU begins after disease progression. Visits should occur at 3-month intervals (± 2 weeks). and	n/d
EOS	EOS is when a subject dies or is lost to follow- up or withdrawal or until 22 June 2017	n/d

n/d Not determinable – since many of these are event driven, the period for an individual subject cannot be determined apriori

Additional description of per protocol analysis

• Exclude subjects with EN 111 or EN 101 or OT 903

This excludes:

a) subjects that did not have NSCLC (OT 903)

b) subjects that did not have metastatic (Stage IV) or advanced stage IIIB with malignant pleural effusion NSCLC (prior to Amendment 3) (ie, subjects that had a lower grade tumor)

• Exclude subjects with EN 117A

This excludes subjects with disease progression prior to study day 1

• Exclude subjects with EN 202

This excludes subjects with a history of or current cancer diagnosis of a cancer type other than NSCLC

• Exclude subjects with EN 109 or EN 117 B

This excludes subject who did not have a baseline pre-chemo scan prior to randomization

- Exclude subjects with an ECOG performance status > 1 at screening (EN 113 or EN 103)
- Exclude subjects with EN 114 or EN 105

This should exclude subjects that had a life expectancy < 6 months based on the judgment of the investigator at screening

- Exclude subjects who received any erythropoiesis stimulating agents within the 28 days prior to screening (EN 223 or 218)
- Exclude subjects with EN 210 This should exclude subjects with a documented history of pure red cell aplasia
- Exclude subjects who are not dosed per protocol through week 7 (however, include subjects who received a planned dose adjustment per section 6.1.2 of the protocol)
- Exclude subjects who did not receive first line chemotherapy with an initial start date on or before Study day 1 and an end date after Study day 1
- Exclude subjects who received ≥ 1 dose of an erythropoiesis stimulating agent(s) other than investigational product as defined in the protocol [eg, epoetin alfa (Procrit, Eprex or Epogen), epoetin beta (Micera), epoetin zeta (Retacrit)] during the treatment period (TA 507)
- Exclude subjects who received the incorrect investigational product (ie, randomized to placebo and received ≥ 1 dose of darbepoetin alfa; or, randomized to darbepoetin alfa and received ≥ 1 dose of placebo

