6.1.3 Missed or Delayed Doses

Investigational product should be administered on the same day Q3W throughout the study. However, if IP cannot be administered as scheduled, every attempt should be made to administer the IP within \pm 6 days of the Q3W schedule. If a dosing visit does not occur within this window, then it is considered a missed dose. No 2 separate IP administrations should occur within a 14-day interval. After a missed or delayed dose,

every attempt should be made to resume dosing according to the original dosing schedule.

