- Amgen's clinical data management department will correct the database for the following eCRF issues without notification to site staff:
 - deletion of obvious duplicate data (eg, same results sent twice with the same date but different clinical planned events—week 4 and early termination)
 - clarifying "other, specify" if data are provided (eg, race, physical examination)

- addition of a leading zero to date and/or time entries if necessary
- deletion of leading and/or trailing spaces to adverse event or concomitant medication terms to facilitate uploading of coded files
- where query responses confirm worsening of a baseline/previous condition but the data field was not updated accordingly by the site, CDM will update AE terms/entries with "worsening"

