6.3 Per Protocol Sets

Since poor adherence to the protocol could have the potential to bias the results towards a conclusion of non-inferiority, a sensitivity analysis will be performed on a per protocol set to confirm results from the primary analysis set. The sensitivity analysis using this per protocol set will be performed for overall survival and **progression free survival**. The per protocol set will include subjects in the primary analysis set who meet all of the following additional criteria **(also see Appendix A):**

- had metastatic (Stage IV) or advanced stage IIIB with malignant pleural effusion (prior to Amendment 3) NSCLC
- no disease progression prior to study day 1
- no history of or current cancer diagnosis other than NSCLC
- had baseline pre-chemo scan prior to randomization (for PFS only)
- had an ECOG performance status of 0 or 1 at screening
- had a life expectancy > 6 months based on the judgment of the investigator at screening
- did not receive erythropoiesis stimulating agents within the 28 days prior to screening
- did not have a documented history of pure red cell aplasia
- dosed per protocol through week 7 with the correctly assigned investigational product (this includes receiving planned doses and dose adjustments per section 6.1.2 of the protocol)
- received first-line cyclic chemotherapy for NSCLC during the treatment period
- did not receive erythropoiesis stimulating agents, other than investigational product as defined in the protocol, during the treatment period.

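### SAP Appendix A lists the Dose 8, 9 and 10 windows 7 days early and the Dose 2 window 1 day early, against its own rule of every 21 days with a 6-day tolerance

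*SAP*

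**What the plan says.** The treatment-period row of the visit-window table in SAP Appendix A states a 21-day cycle with a tolerance of 6 days either way, and its interval column gives 15-27 days between doses. It then lists windows dose by dose. The entries that matter here are:

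- "Dose 2: study day 22 (15-27")
- "Dose 7: study day 127 (121-133")
- "Dose 8: study day 141 (135-147")
- Dose 9 at day 162 (156-168) and Dose 10 at day 183 (177-189), after which the list is left open.

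The protocol's Schedule of Assessments (Appendix A) gives the same cycle in weeks: "Q3W (± 6 days) (eg, Wk 4, 7, 10, 13, 16, 19, 22, 25, 28"). The SAP's list of definitions counts study week 1 as the 7 days starting on study day 1. Protocol Section 6.1.3 asks sites to return to the original schedule after a missed or delayed dose, so the target days do not drift.

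**The concern.** The list contradicts the rule at the head of its own row. Dose 7 to Dose 8 is a 14-day step, and the next two rows inherit the 7-day shift. The Dose 2 limits are also not centered on their target.

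The table has a column for window definitions and sits in an appendix of technical detail for the statistical programs, so a programmer could reasonably implement it. A subject dosed and sampled on the exact scheduled day for Dose 8, 9 or 10 would then match no visit, and neither would anyone up to 6 days late. The SAP does not say what happens to a value outside every window. The output at stake is hemoglobin over time (SAP Section 9.5.3). SAP Section 12 puts hemoglobin-over-time plots among the first-priority outputs, due 2-3 business days after database lock.

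**Working it through.** **Inputs.** Dose 1 on day 1, 21-day cycle, tolerance 6 days (SAP Appendix A). Visit weeks 4, 7, ..., 22, 25, 28 (protocol Appendix A). Week w starts on day 1 + 7(w - 1) (SAP definitions).

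**Step 1: reproduce the table.** Target day of dose k = 1 + 21(k - 1). For k = 1 to 7 this gives 1, 22, 43, 64, 85, 106, 127, exactly as listed. Target plus or minus 6 also gives the listed windows for Doses 3-7 exactly, and for Dose 1 when cut off at day 1.

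**Step 2: the rows that do not reproduce.**

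| Dose | Listed | By the rule | Shift in target | Shift in limits |
|---|---|---|---|---|
| 2 | 22 (15-27) | 22 (16-28) | 0 | -1 |
| 8 | 141 (135-147) | 148 (142-154) | -7 | -7 |
| 9 | 162 (156-168) | 169 (163-175) | -7 | -7 |
| 10 | 183 (177-189) | 190 (184-196) | -7 | -7 |

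**Step 3: check against the protocol weeks.** Week 22: 1 + 7 × 21 = 148. Week 25: 1 + 7 × 24 = 169. Week 28: 1 + 7 × 27 = 190. The listed days 141, 162 and 183 are the first days of weeks 21, 24 and 27.

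**Step 4: slip or convention?** Each shifted row is consistent within itself (141, 162 and 183, each plus or minus 6), so garbled text is not the cause. From Dose 3 on, 8 days separate consecutive windows (for example days 50-57), except between Doses 7 and 8, where only day 134 does. The Dose 2 limits repeat the interval column's 15-27 as if they were study days; 15-27 days after day 1 is days 16-28.

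**Step 5: coverage, counted as dosing days.** Each permitted day was compared with all ten listed windows.

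- Doses 8, 9 and 10: days 148-154, 169-175 and 190-196 are in no window. That is the on-time day plus six late days, 7 of 13 each. The six early days (142-147, 163-168, 184-189) fall in the right window.
- Dose 2: day 28 is in no window, and day 15 is included although it is 7 days before the target.
- Doses 3-7: 13 of 13 covered.

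**Step 6: coverage, counted as sampling days.** The protocol (Section 7.1.12) and a note in the same SAP row allow samples up to 1 day before dosing, so permitted sampling days run from target - 7 to target + 6. For Dose 8 that is 141-154, of which the listed window holds 141-147. An on-time visit sampled the day before, on day 147, is captured; one sampled on day 148 is not. For Dose 2 the range is 15-28, so day 15 is a legitimate sampling day and only day 28 is missed.

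**Step 7: after Dose 10.** Continuing in 21-day steps from 183 puts Dose 11 at day 204 (198-210). The rule gives 1 + 21 × 10 = 211 (205-217), so days 211-217 would be uncovered.

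**The case against.** The best reply is that little depends on this table. The SAP never says that it assigns values to visits. Protocol Section 13.3 shows that the database carries visit labels, since it describes results entered under "different clinical planned events", and the analysis may rely on those. Both objections stand, and they make the consequence conditional. The rows themselves remain wrong.

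A reader might also infer more than the documents support:

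- **That every on-time hemoglobin value is lost.** This is not so, because a sample taken the day before an on-time dose is still captured (Step 6).
- **That membership of the per-protocol set is altered.** SAP Section 6.3 requires subjects to be "dosed per protocol through week 7 with the correctly assigned investigational product", and Appendix A repeats this as "Exclude subjects who are not dosed per protocol through week 7". If the Dose 2 window were the test, a permitted day-28 dose would count as a deviation. Neither passage refers to the window table, however. Section 6.3 points to protocol Section 6.1.2, and the protocol's own tolerance in Section 6.1.3 allows day 28. The documents support only a request to clarify.
- **That the table conflicts with the protocol's minimum spacing**, "No 2 separate IP administrations should occur within a 14-day interval". Listed Dose 8 days 135-140 are 8-13 days after an on-time Dose 7. But a window classifies dates and does not order doses, and correctly listed windows also admit close pairs (days 49 and 58 are 9 days apart). This adds little to the visit weeks.

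**Conclusion.** The table is wrong as written, and the point is minor. Doses 8, 9 and 10 are 7 days early in target and both limits; the Dose 2 limits are 1 day early. Both follow from the row's own rule, and the protocol's visit weeks confirm the later targets.

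The effect rests on one assumption that the documents do not settle: that the table is used to assign values to visits. If it is, the descriptive hemoglobin-over-time plots from week 22 on would drop some on-time and all of the late-visit values dated in the uncovered days. The documents do not say how many subjects are still treated by then, so no overall loss can be given.

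Not affected are the primary analyses of OS and PFS, the transfusion or hemoglobin endpoint from day 29 to the end of the efficacy treatment period, and the week 13 and 16 hemoglobin summaries (days 85 and 106, Doses 5 and 6, both dated correctly).

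**What to change.** Reconcile the SAP windows with the stated schedule:

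1. As dosing windows, use day 1 + 21(k - 1), plus or minus 6: Dose 2, 16-28; Dose 8, 142-154; Dose 9, 163-175; Dose 10, 184-196. Replace the open-ended last entry with this rule.
2. Where the windows classify samples or other evaluations, start each one a day earlier to match the permitted sampling (for example Dose 2, 15-28; Dose 8, 141-154). A plain change of Dose 2 to 16-28 would drop a permitted sampling day.
3. State whether this table or the database's visit labels assign values to visits, and whether the table is used in the per-protocol dosing check through week 7.

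The cost is a table correction and two clarifying sentences in the SAP. No new data are needed, and only analysis windows change, not the dosing schedule.
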